5.3.1. Joint Counts

- Tender joint count (TJC)

TJC is defined as the number of tender joints with abnormality. In case of missing joint assessment, the TJC will be prorated as follows:

$28 * (\text{number of joints with tender score as "Present"}) / (\text{number of non-missing tender joints})$.

Joints with a response of "Not Done" or "Not Applicable" will be handled as missing. If less than 20 joints have non-missing tender scores, then TJC will be defined as missing.

- Swollen joint count (SJC)

SJC is defined as the number of swollen joints with abnormality. In case of missing joint assessment, the SJC will be prorated as follows:

$28 * (\text{number of joints with swollen score as "Present"}) / (\text{number of non-missing swollen joints})$.

Joints with a response of "Not Done" or "Not Applicable" will be handled as missing. If less than 20 joints have non-missing swollen scores, then SJC will be defined as missing.

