7.5. Assessments of Disease Activity

Individual components for the following indicators of disease activity will be collected throughout the study as described in [Table 3](#) below.

Table 3. Disease Activity Indicators

Indicator	Definition/Calculation
DAS28-4 (CRP)	$0.56*\sqrt{(TJC28)} + 0.28*\sqrt{(SJC28)} + 0.36*\ln(\text{CRP in mg/l} + 1) + 0.014*\text{PtGA in mm} + 0.96$
DAS28-4 (ESR)	$0.56*\sqrt{(TJC28)} + 0.28*\sqrt{(SJC28)} + 0.70*\ln(\text{ESR in mm/ hour}) + 0.014*\text{PtGA in mm}$
Simplified Disease Activity Index (SDAI)	$(28TJC) + (28SJC) + [\text{PhyGA in cm}] + [\text{PtGA in cm}] + [\text{CRP in mg/dL}]$
Clinical Disease Activity Index (CDAI)	$(28TJC) + (28SJC) + [\text{PhyGA in cm}] + [\text{PtGA in cm}]$
American College of Rheumatology (ACR) Response Rates	The ACR's definition for calculating a 20% improvement in RA (ACR20) is as follows: a 20% improvement in tender and swollen joint counts and 20% improvement in 3 of the 5 remaining ACR-core set measures: subject and physician global assessments, pain, disability, and an acute-phase reactant (eg, CRP). Similarly, ACR50 and 70 are calculated with the respective percent improvements.
ACR/EULAR Boolean-based definition of remission	At any time point, a subject must satisfy all of the following: tender joint count ≤ 1 , swollen joint count ≤ 1 , CRP ≤ 1 mg/dL, subject's global assessment of health ≤ 1 on a 0-10 scale

TJC = tender joint count; SJC = swollen joint count; CRP = C-reactive protein in mg/L; ESR = erythrocyte sedimentation rate in mm/first hour, PtGA = subject's global assessment of health; PhyGA = physician's global assessment of health

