7.6. Joint Counts

7.6.1. Tender/Painful Joint Count (28 Joint Count)

Twenty-eight (28) joints will be assessed by a blinded joint assessor to determine the number of joints that are considered tender or painful. The response to pressure/motion on each joint will be assessed using the following scale: Present/Absent/Not Done/Not Applicable (to be used for artificial joints).

The 28 joints to be assessed are the shoulders, elbows, wrists, metacarpophalangeal (MCP) joints, proximal interphalangeal (PIP) joints, and knees. Artificial joints will not be assessed.

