3.2. Secondary Efficacy Endpoint(s)

- Change in the DAS28-4(ESR) from Week 24 to Week 36;
- Changes in the DAS28-4 (CRP), CDAI and SDAI, respectively, from Week 24 to Week 48 and from Week 24 to Week 36;
- LDA as assessed by DAS28-4(ESR) ≤ 3.2, DAS28-4(CRP) ≤ 3.2, CDAI ≤ 10 and SDAI ≤ 11, respectively, at Weeks 48 and 36;
- Remission as assessed by ACR-EULAR Boolean remission criteria, DAS28-4 (ESR) < 2.6, DAS28-4 (CRP) < 2.6, CDAI ≤ 2.8 and SDAI ≤ 3.3, respectively, at Weeks 48 and 36;
- ACR20, ACR 50, and ACR70 responses, respectively, at Weeks 48 and 36;

- Change in the HAQ-DI, the SF-36 (8 domain scores and 2 component scores), WPAI, EuroQol EQ-5D and the FACIT-Fatigue scale score, respectively, from Week 24 to Week 48 and from Week 24 to Week 36;
- HAQ-DI response (ie, decrease of at least 0.22) at Weeks 48 and 36.
- Note:
- For subjects entering the double-blind phase, the value at randomization (Week 24) for each endpoint is the last nonmissing observation before the first dose of study drug in double-blind phase.
- The baseline (Day 1) value for each endpoint is the last nonmissing observation before the first dose of study drug in open-label run-in phase.
- ACR20, ACR 50, ACR70, and HAQ-DI responses are relative to baseline (Day 1).

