9. APPENDICES

Appendix 1. DATA DERIVATION DETAILS

Appendix 1.1. Endpoints Definition and Derivation

Endpoint	Defination/Calculation
DAS28-4 (CRP)	$0.56*\sqrt{(TJC28)} + 0.28*\sqrt{(SJC28)} + 0.36*\ln(\text{CRP in mg/l} + 1) + 0.014*\text{PtGA in mm} + 0.96$
DAS28-4 (ESR)	$0.56*\sqrt{(TJC28)} + 0.28*\sqrt{(SJC28)} + 0.70*\ln(\text{ESR in mm/ hour}) + 0.014*\text{PtGA in mm}$
SDAI	$(28TJC) + (28SJC) + [\text{PhyGA in cm}] + [\text{PtGA in cm}] + [\text{CRP in mg/dL}]$
CDAI	$(28TJC) + (28SJC) + [\text{PhyGA in cm}] + [\text{PtGA in cm}]$
ACR20/50/70 responder	ACR20: at least 20% improvement in tender and swollen joint counts and at least 20% improvement in at least 3 of the 5 remaining ACR-core set measures: subject and physician global assessments, pain, HAQ-DI, and CRP. Similarly, ACR50 and 70 are calculated with the respective percent improvements.
ACR/EULAR Boolean-based definition of remission	all of the following satisfied: $TJC \leq 1$, $SJC \leq 1$, $CRP \leq 1$ mg/dL, $PtGA \leq 1$ on a 0-10 scale
LDA of DAS28-4 (CRP)	$DAS28-4 (CRP) \leq 3.2$
LDA of DAS28-4 (ESR)	$DAS28-4 (ESR) \leq 3.2$
LDA of SDAI	$SDAI \leq 11$
LDA of CDAI	$CDAI \leq 10$
Remission of DAS28-4 (CRP)	$DAS28-4 (CRP) < 2.6$
Remission of DAS28-4 (ESR)	$DAS28-4 (ESR) < 2.6$
Remission of SDAI	$SDAI \leq 3.3$
Remission of CDAI	$CDAI \leq 2.8$
HAQ-DI responder	Decrease ≥ 0.22
RAPID3	$(\text{HAQ} * 3.33 + \text{pain VAS in mm/10} + \text{PtGA in mm/10})/3$.

TJC = tender joint count; SJC = swollen joint count; CRP = C-reactive protein in mg/L; ESR = erythrocyte sedimentation rate in mm/first hour, PtGA = subject's global assessment of health; PhyGA = physician's global assessment of health, HAQ-DI = Health Assessment Disability Questionnaire-Disability Index; LDA = Low Disease Activity. RAPID3 = Routine Assessment of Patient Index Data 3.

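### Prorated joint counts are not rounded before the Boolean remission limit of 1 is applied, so a subject with an artificial joint and one involved joint on that scale cannot meet it

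*SAP*

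**What the plan says.** Protocol 7.6.1 and 7.6.2 give each of the 28 joints a score for tenderness and one for swelling, and reserve the answer Not Applicable for prostheses: "Artificial joints will not be assessed". Subjects with a prosthesis can enrol, because exclusion criterion 3c in Protocol 4.2 bars only an infected prosthesis still in place.

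SAP 5.3.1 says "Joints with a response of 'Not Done' or 'Not Applicable' will be handled as missing". It then scales each count to 28 joints: "In case of missing joint assessment, the TJC will be prorated as follows" and, separately, "In case of missing joint assessment, the SJC will be prorated as follows". Each formula is 28 times the joints scored Present, divided by the joints scored on that scale. There is a floor: "If less than 20 joints have non-missing tender scores, then TJC will be defined as missing", with a matching rule for swelling. No rounding is mentioned.

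SAP Appendix 1.1 defines Boolean remission as "all of the following satisfied": TJC, SJC, CRP in mg/dL and patient global on a 0-10 scale, each at most 1. It uses the same variable names and does not say whether the prorated or the observed count is meant. Protocol 7.5, Table 3 sets the same limits ("At any time point, a subject must satisfy all of the following: tender joint count" and so on) and does not mention prorating.

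SAP 3.2 lists "Remission as assessed by ACR-EULAR Boolean remission criteria" as a secondary endpoint at Weeks 48 and 36. SAP 3.3 lists it again for the run-in at Weeks 12 and 24.

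**The concern.** The Boolean criterion is a whole-number limit: one tender joint and one swollen joint are allowed. Prorating turns a count of one into a value just above one whenever a joint on that scale was not scored. Read as written, the SAP allows one involved joint to a subject with all 28 joints scored and none to a subject with a knee replacement. A prosthesis is permanent, so that subject meets the stricter limit at every visit.

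Against the observed count the shift goes one way, because prorating never lowers a count. The remission rate can only be reduced relative to the definition in Protocol Table 3. Since the SAP does not address rounding, two programmers could also derive different remission rates from the same data.

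**Working it through.** **Inputs**
- Prorated count = 28 × k / m, where k is the number of involved joints and m the number scored on that scale (SAP 5.3.1).
- Prorating applies for m = 20 to 27; below 20 the count is missing (SAP 5.3.1).
- Limit: TJC ≤ 1 and SJC ≤ 1 (SAP Appendix 1.1; Protocol Table 3).

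The documents give no figure to reproduce on this point.

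**Step 1. One and two involved joints**

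| m scored | 28 × 1 / m | Meets ≤ 1? | Rounded | 28 × 2 / m | Rounded |
|---|---|---|---|---|---|
| 28 | 1.000 | yes | 1 | 2.000 | 2 |
| 27 | 1.037 | no | 1 | 2.074 | 2 |
| 26 | 1.077 | no | 1 | 2.154 | 2 |
| 25 | 1.120 | no | 1 | 2.240 | 2 |
| 24 | 1.167 | no | 1 | 2.333 | 2 |
| 23 | 1.217 | no | 1 | 2.435 | 2 |
| 22 | 1.273 | no | 1 | 2.545 | 3 |
| 21 | 1.333 | no | 1 | 2.667 | 3 |
| 20 | 1.400 | no | 1 | 2.800 | 3 |

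With no involved joint the count stays 0 and passes. For every m from 20 to 27 the limit therefore works as 0.

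**Step 2. Does rounding admit anyone it should not?** After rounding, one involved joint always gives 1 and passes; two always give 2 or 3 and fail. For this test, rounding classifies exactly as the observed count does when at least 20 joints are scored.

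**Step 3. Other indices.** For one involved joint, prorating adds 28/27 − 1 = 0.04 to 28/20 − 1 = 0.40 to CDAI or SDAI. To DAS28 it adds 0.56 × (√1.037 − 1) = 0.01 to 0.56 × (√1.4 − 1) = 0.10 if the joint is tender, and half of that if it is swollen. A cut-off changes only for a subject very close to it. Example: 27 joints scored, one tender, one swollen, global scores summing to 0.75 cm. Observed counts give CDAI = 2 + 0.75 = 2.75, which meets ≤ 2.8. Prorated counts give 2 × 1.037 + 0.75 = 2.82, which does not.

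**Step 4. Size.** The documents give neither the share of subjects with a non-assessable joint nor the share of remitters with exactly one involved joint. Assume 3% to 10% and 20% to 40%.
- Share of Boolean remissions lost: 0.03 × 0.20 = 0.6% to 0.10 × 0.40 = 4%.
- Assume further a Boolean remission rate of 20% to 30% among 232 randomized subjects: 46 to 70 remitters. The loss is 0.006 × 46 = 0.3 to 0.04 × 70 = 2.8 subjects over both arms.
- Sensitivity: with 2% to 20% of subjects having a missing joint, the rate falls by 0.02 × 0.20 × 0.20 = 0.08 to 0.20 × 0.40 × 0.30 = 2.4 percentage points.

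**The case against.** Several points on the other side stand, and they limit what may be said.

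- **Scope of failure.** A reader might infer that any subject with an unassessed joint and one involved joint always fails. The documents do not support that. TJC and SJC are prorated separately, so a subject with 28 tenderness scores, one tender joint, one Not Done swelling score and no swollen joint has TJC = 1 and SJC = 0, and passes both joint limits. With fewer than 20 joints scored, the count is missing rather than inflated. The subject is then handled by non-responder imputation or leaves the observed-cases analysis.
- **Not Done joints.** A reader might infer that every such failure is a true remission lost. If a natural joint was not examined, an observed count of 1 is a lower bound, and the failure may be correct. The claim is firm only for prostheses, and only when CRP, patient global and the other joint count also meet their limits.
- **Silence on rounding.** The SAP does not prescribe unrounded values; it says nothing. Unrounded is the plain reading of the formula, but a programmer could round. This changes the description of the gap and leaves the need for a stated rule.
- **Other thresholds.** The inflation is not confined to the Boolean test, as the CDAI example shows. The difference is one of degree: in the Boolean test any excess over 1 decides the result, whereas CDAI and SDAI cut-offs change only very near the threshold.
- **Consequence.** Boolean remission is one of five remission definitions among many secondary endpoints.

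None of these removes the core case. For a subject with a prosthesis and one involved joint on that scale, following the SAP formula gives a different answer from Protocol Table 3, and no other section corrects it.

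**Conclusion.** The point holds in limited form. With 20 to 27 joints scored on a scale, the SAP as written reduces the Boolean limit on that scale from 1 to 0. This misclassifies subjects with artificial joints who meet every other component.

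The arithmetic rests on the documents alone; the size rests on the assumed prevalences. On those, about 0.6% to 4% of Boolean remissions are lost, at most a few subjects in the double-blind phase and at the low end fewer than one.

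A reader might infer a biased treatment comparison or a threat to the non-inferiority conclusion. The documents support neither. Both arms use the same rule, and the primary test in SAP 5.1 compares mean change in DAS28-4 (ESR) with 0.6 and does not use this limit. This is a minor correction, worth making because it is cheap and removes an ambiguity in a secondary endpoint.

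**What to change.** Add one sentence to the Boolean remission row of SAP Appendix 1.1, with a cross-reference from 5.3.1: for this criterion only, prorated TJC and SJC are rounded to the nearest whole joint before comparison with 1. Applying the limit to the observed count when at least 20 joints are scored is equivalent. Keep unrounded prorated values for DAS28, CDAI, SDAI and ACR.

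The cost is one sentence and one programming step, with no new data. There are two small downsides. The joint count then exists in two versions, so a subject-visit could carry 1 for Boolean remission and 1.037 for CDAI. And a subject whose unexamined Not Done joint is in fact involved could be counted as in remission.

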5.3.2. DAS28-4(ESR), DAS28-4(CRP), CDAI, SDAI

DAS28-4(ESR) is a derived variable from 4 components. If any component is missing, DAS28-4(ESR) will be missing.

Above approach will also be used for DAS28-4(CRP), CDAI, SDAI.

5.3.3. LDA and Remission

The binary variables derived from the continuous endpoints (such as DAS28-4 (ESR)) will be imputed using Non-Responder Imputation (NRI) method. Missing values due to a patient dropping from the study for any reason (eg, lack of efficacy or adverse event) will be handled by setting the the response value to nonresponsive from that visit onward. This also means that if a patient withdraws at a visit but had responsive values at that visit, the binary variable is still set to nonresponsive.

NRI approach will be used to impute the missing data of LDA as assessed by:

- DAS28-4(ESR) ≤ 3.2 ;
- DAS28-4(CRP) ≤ 3.2 ;
- CDAI ≤ 10 ;
- SDAI ≤ 11 .

and Remission as assessed by:

- ACR-EULAR Boolean remission criteria;
- DAS28-4 (ESR) < 2.6 ;
- DAS28-4 (CRP) < 2.6 ;
- CDAI ≤ 2.8 ; and
- SDAI ≤ 3.3 .

For subjects who don't enter the blinded MTX withdrawal phase, the imputation is only applied up to Week 24.

5.3.4. ACR20, ACR50, ACR70

Because the ACR20, ACR50, ACR70 variables are based on several component variables, it is possible that the values may still be calculated even if the component variables have some missing values. In this case, no imputation method is needed. If the ACR value is still missing, an imputation method will be applied.

If the ACR value is missing due to missing values in any of the components, while the patient is still enrolled, the method of last observation carried forward (LOCF) will be used to carry forward any of the missing components, and from that mix of actual and carried-forward values, the values of ACR20, ACR50 and ACR70 will be determined.

This type of LOCF method will be known as "LOCF mixed components," since it is based on calculating the composite value based on a mixture of values at a visit and values carried forward from previous visits. It can be justified as an attempt to carry forward as little information as possible.

After the LOCF imputation has been applied, missing values due to a patient dropping from the study for any reason (eg, lack of efficacy or adverse event) will be handled by setting the ACR value (ACR20, ACR50 and ACR70) to nonresponsive from that visit onward. This also means that if a patient withdraws at a visit but had responsive ACR values at that visit, the ACR value is still set to nonresponsive. This method also goes by the name Non-Responder Imputation, NRI.

It is also the case that LOCF method does not carry forward any baseline values, as a convention. That is, a value carried forward must be a post-baseline value. If there are no post-baseline values that are non missing, the component remains missing.

Regardless of any imputation or none, if for some reason the ACR value still can't be determined, including the case where baseline data is missing, then its value will be set to non-responder.

For subjects who don't enter the blinded MTX withdrawal phase, the imputation is only applied up to Week 24.

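### SAP 5.3.4 bars only Day 1 values from carry-forward, so ACR components measured before MTX withdrawal can fill gaps at Weeks 36 and 48

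*SAP*

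**What the plan says.** SAP 5.3.4 sets out the imputation for ACR20, ACR50 and ACR70. It starts from the case "If the ACR value is missing due to missing values in any of the components, while the patient is still enrolled" and fills the missing components by LOCF. The response is then computed from "a mixture of values at a visit and values carried forward from previous visits". The one restriction on the source is that baseline values are not used: "That is, a value carried forward must be a post-baseline value".

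SAP 3.2 fixes what baseline means: "The baseline (Day 1) value for each endpoint is the last nonmissing observation before the first dose of study drug in open-label run-in phase". The same note defines the value at randomization (Week 24) separately, and makes ACR response relative to Day 1 at every visit.

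Two other rules in 5.3.4 matter. After LOCF, "missing values due to a patient dropping from the study for any reason" are scored as non-response. And the section's only limit tied to Week 24 is this: "For subjects who don't enter the blinded MTX withdrawal phase, the imputation is only applied up to Week 24". It does not apply to randomized subjects.

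SAP 6.2.6 analyses double-blind ACR response with the 5.3.4 rule, labelled there simply as NRI, and also on observed cases.

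**The concern.** Barring baseline values from LOCF keeps pre-treatment data out of the treatment period. That is sufficient when subjects are randomized on Day 1. Here the randomized comparison starts at Week 24, when the monotherapy arm stops MTX completely and without tapering (Protocol 5.5). For that comparison Week 24 is the pre-treatment value, yet the rule treats it as an ordinary post-baseline observation.

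Carried Week 24 values are also favourable by selection, because only subjects with CDAI of 10 or less are randomized (Protocol 4.3). In the continued-MTX arm they come from the regimen the subject is still taking. In the monotherapy arm they come from the regimen that was withdrawn. At stake is whether the ACR results at Weeks 36 and 48 show what happens after withdrawal. LDA, remission and HAQ-DI response (SAP 5.3.3 and 5.3.5) use non-responder imputation without this LOCF step.

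**Working it through.** No figure in the plan depends on this rule, so there is none to reproduce. The check is of the text, followed by an illustration on assumed rates.

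**1. Which values are eligible.** The Schedule of Activities collects ACR components on Day 1 and at Weeks 12, 24, 36 and 48. With baseline fixed at Day 1, Weeks 12 and 24 are post-baseline. SAP Appendix 1.2 takes the randomization value from observations up to and including the first double-blind dosing date, so it reflects tofacitinib plus MTX. For a component missing at Week 36, the last observation is normally Week 24, or Week 12 if Week 24 is also missing. At Week 48 it is Week 24 only if Week 36 is missing too. Nothing in SAP 5.3.4, 6.2.6 or Appendix 1.2 stops this at randomization.

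**2. How a gap can arise in an enrolled subject.** A joint count is missing if fewer than 20 joints are scored (SAP 5.3.1). Appendix 1.2 also excludes efficacy data collected more than 7 days off study drug, while Protocol 6.3 discontinues subjects only after more than 14 consecutive days off. If excluded data count as missing, a visit 8 to 14 days off drug would also be open to carry-forward.

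**3. One subject (invented values), ACR50.**
- Day 1: TJC 12, SJC 10, pain and both globals 60 mm, HAQ-DI 1.5, CRP 15.
- Week 24: TJC 3, SJC 2, pain and both globals 20 mm, HAQ-DI 0.5, CRP 4. CDAI = 3 + 2 + 2 + 2 = 9, so the subject can be randomized, and is an ACR50 responder.
- Week 36, true state: TJC 9 (25% better), SJC 7 (30% better), pain and subject global 28 mm (53% better), HAQ-DI 0.75 (50% better), physician global 45 mm, CRP 12. Three of the five other measures reach 50% but the joint counts do not: not an ACR50 responder.
- If the Week 36 joint counts are missing, the rule carries TJC 3 and SJC 2, and the subject is scored an ACR50 responder.

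**4. Arm level.** Let p be the true response rate, m the share still enrolled with the whole ACR set missing, and q the Week 24 response rate among them. If missingness is unrelated to outcome:
- current rule: rate = (1 - m)p + mq
- carry-forward barred across randomization, non-responder otherwise: rate = (1 - m)p

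The rules differ by mq in each arm, so the between-arm differences differ by mq(monotherapy) minus mq(continued MTX).

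Assumptions: p = 50% monotherapy and 60% continued MTX (true difference -10.0 points), q = 70-90%.

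*Equal m and q.* The difference is (1 - m) x (-10.0) under **both** rules: -9.8 at m = 2%, -9.5 at 5%, -9.0 at 10%. Only the arm rates move. At m = 5% and q = 70% they are 51.0% and 60.5% under the current rule, against 47.5% and 57.0% with the restriction. With 116 per arm (232/2), that is 116 x 0.05 x 0.70 = 4.1 carried responders per arm.

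*m in the monotherapy arm only, unrelated to outcome:*

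| m | Current rule | With restriction |
|---|---|---|
| 2% | -9.6 to -9.2 | -11.0 |
| 5% | -9.0 to -8.0 | -12.5 |
| 10% | -8.0 to -6.0 | -15.0 |

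*m = 5% in the monotherapy arm only, all of them truly non-responders.* Current rule: 50 + 5 x 0.70 = 53.5% up to 50 + 5 x 0.90 = 54.5%, a difference of -6.5 to -5.5. With the restriction: 50.0%, difference -10.0. Observed cases: 50/95 = 52.6%, difference -7.4.

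**The case against.** The strongest objection is that the restriction need not alter the comparison. With equal missingness and equal Week 24 response in the two arms, carry-forward and non-responder scoring give the same difference. **This stands.** A reader might infer that carrying a common Week 24 value always pulls the arms together and that barring it would undo the shrinkage. The documents do not support that: giving both arms any common imputed value shrinks the difference by the same factor, and they give no missing-data rates by arm.

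The SAP also does not breach its own convention. It says only that baseline values are not carried, and ACR response is defined against Day 1. **This stands too:** the point is a gap in the rule for this design, not a contradiction.

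The affected set is narrow. Dropouts become non-responders, ACR must be undeterminable from the observed components, and the Week 36 window runs from the day after randomization to day 126, with each component windowed separately. Losing the whole set is therefore the extreme case. **This limits the size but does not close the gap.**

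The observed-cases analysis in SAP 6.2.6 uses no carried values and sits beside the imputed one. It exposes the effect only in part: when missingness follows worsening it is biased in the same direction, as the -7.4 above shows.

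Finally, the different handling of ACR and of LDA or remission can be defended as a design choice for a seven-component response. That is fair, and the point does not rest on the inconsistency.

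**Conclusion.** The point holds as a gap in a secondary-endpoint rule. As written, SAP 5.3.4 allows a monotherapy subject to be scored an ACR responder at Week 36, and less often at Week 48, on components measured before MTX was withdrawn. Relative to non-responder handling it raises the ACR rates in both arms. It understates loss of response after withdrawal when missingness is more common in the monotherapy arm (with carried response above the arm's true rate) or follows worsening. With equal, non-informative missingness and equal Week 24 response, the between-arm difference is the same under either rule.

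The size cannot be derived from the documents. With 5% missing in monotherapy only and the assumed rates above, the understatement is 1.0 to 2.0 points if missingness is unrelated to outcome, and 3.5 to 4.5 points if all the missing are non-responders. Gaps in single components would matter less.

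A reader might also infer that the non-inferiority conclusion is at risk. It is not: the primary DAS28-4(ESR) MMRM uses observed data without this LOCF, and no margin is set for ACR. This is a cheap improvement, not a threat to the trial's main result.

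**What to change.** Add to SAP 5.3.4: for Weeks 36 and 48, only components measured after the first double-blind dose may be carried forward; if ACR status still cannot be determined, the subject is a non-responder. The fallback is already the section's last resort. Report, by arm and visit, how many ACR values used a carried component, and describe the method in SAP 6.2.6 as LOCF of components followed by NRI.

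The cost is one sentence, one programming condition and one count table. The downside is slightly more imputed non-responders in both arms. That lowers the ACR rates and can overstate the difference when missingness is unequal but unrelated to outcome (-12.5 against a true -10.0 at 5% missing in monotherapy only). The observed-cases analysis should therefore stay beside it.
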